5.2.3.2 Concomitant Therapy

All medications (including, but not limited to, prescription or over-the-counter medicines such as aspirin, antacids, vitamins, mineral supplements, and herbal preparations) that the subject is receiving from Baseline through the end of the study, must be recorded on the appropriate electronic Case Report Form (eCRF) along with the reason for use, dates of administration including start and end dates, and dosage including dose, frequency and route of administration.

Subjects will be allowed two periocular corticosteroid injections per eye per year during the duration of the study at the investigator's discretion. No intraocular or intravitreal injections will be allowed.

Subjects will be allowed to continue on one ongoing non-biologic protocol-permitted immunosuppressive therapy and one systemic corticosteroid at study entry. Alternatively, if the subject has not been on a non-biologic immunosuppressive previously, they can add one of the following at any time during the Study M11-327. In addition, doses must be within the acceptable limits listed below:

- Methotrexate (MTX) \leq 25 mg per week

- Cyclosporine \leq 4 mg/kg per day
- Mycophenolate mofetil \leq 2 grams per day or an equivalent drug to mycophenolate mofetil (e.g., mycophenolic acid) at an equivalent dose approved by the Medical Monitor
- Azathioprine \leq 175 mg per day
- Tacrolimus (oral formulation) \leq 8 mg per day

The non-biologic immunosuppressive drug and/or corticosteroids can be initiated, changed or discontinued during the course of the study if it is considered appropriate for the subject in the investigator's expert opinion.

Dosage of topical eye drops (including topical corticosteroid eye drops) may be initiated or adjusted as medically necessary during the study.

The initiation, discontinuation and/or changes in dosing of these non-biologic immunosuppressive therapies and corticosteroids can have an impact on uveitis. However, the intent of allowing these to occur, is to reflect standard clinical practice in the management of uveitis.

Each vaccine administered to the subject should be listed as a concomitant medication on the Other Medications eCRF. Live vaccines may not be given concurrently while on study drug or for 70 days after the last dose of adalimumab.

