5.2.3.3 Prohibited Therapy

With the exception of one allowed concomitant immunosuppressant, systemic/topical/periorcular (per eye) corticosteroids as detailed in Section 5.2.3.2, the introduction of other medications for uveitis is prohibited during the study.

The following medications are prohibited during the study:

- All biologic therapies with a potential therapeutic impact on non-infectious uveitis, including but not limited to the following:
 - Enbrel[®] (etanercept);

- Remicade[®] (infliximab);
- Simponi[®] (golimumab);
- Orencia[®] (abatacept);
- Kineret[®] (anakinra);
- Rituxan[®]/MabThera[®] (rituximab);
- Tysabri[®] (natalizumab);
- Actemra[®]/RoActemra[®] (tocilizumab);
- Raptiva[®] (efalizumab);
- Cimzia[®] (certolizumab pegol);
- Stelara[®] (ustekinumab);
- Benlysta[®] (belimumab);
- Anti-VEGF therapy
- Live vaccines (during the study and for 70 days after the last dose of study drug) (including but not limited to the following: monovalent live attenuated influenza A (H1N1) [intranasal], seasonal trivalent live attenuated influenza (intranasal), herpes zoster, rotavirus, varicella (chicken pox), measles-mumps-rubella (MMR) or MMRV (measles-mumps-rubella-varicella), oral polio vaccine (OPV), smallpox, yellow fever, Bacillus Calmette-Guerin (BCG) and typhoid
- Rifampin/Pyrazinamide combination
- Anti-retroviral therapy
- All other immunosuppressive therapy other than MTX, cyclosporine, mycophenolate mofetil or an equivalent drug to mycophenolate mofetil (e.g., mycophenolic acid), azathioprine, and tacrolimus (oral formulation)
- Intraocular or intravitreal corticosteroid injections
- Ozurdex[®] (dexamethasone implant)
- Intravitreal MTX
- Medical or recreational marijuana
- Systemic carbonic anhydrase inhibitor

- Any TB-prophylaxis therapy (except for those subjects who entered the parent study prior to Study M10-877 Amendment 6 or Study M10-880 Amendment 7 and were still taking TB-prophylaxis when they entered Study M11-327)
- Retisert[®] (glucocorticosteroid implant)
- Cyclophosphamide
- Chlorambucil

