## **7.5 Concomitant Medications**

Medications with a start date prior to or on the first dose of adalimumab in Study M11-327 and a stop date on or after the first dose of adalimumab in Study M11-327 or a missing stop date will be considered as concomitant medications at baseline of Study M11-327. If the start date is missing and the stop date is on or after the baseline date in Study M11-327, or if start and stop dates are both missing, the medication will also be considered as concomitant at baseline in Study M11-327. The following therapies used by subjects at baseline in Study M11-327 will be summarized by counts and percentages:

- Immunosuppressants (IMMs)
  - Azathioprine

- Cyclosporine
- Methotrexate (MTX)
- Mycophenolate mofetil or equivalent drug (e.g. mycophenolic acid)
- Tacrolimus
- Corticosteroids (CSs)
  - Oral corticosteroids
  - Topical corticosteroids
  - Other corticosteroids

Concomitant medication is defined as any medication that started prior to the first dose of adalimumab in Study M11-327 and continued to be taken after the first dose of adalimumab in Study M11-327 or any medication that started after the first dose of adalimumab in Study M11-327, but not after the last dose of adalimumab in Study M11-327. The number and percentage of subjects who had taken concomitant medications will be summarized by generic drug name based on the World Health Organization (WHO) drug dictionary.

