- Change in dose of IMM at each study time point relative to baseline for subjects who had inactive uveitis when they entered the study and to Week 8 for subjects who had active uveitis when they entered the study only in subjects on IMMs at baseline/Week 8 of Study M11-327.
- Proportion of subjects who started systemic CS in Study M11-327.
- Systemic CS dose at each study time point.
- Proportion of subjects at each study time point with

- Systemic CS dose = 0 mg/day
- Systemic CS dose > 0 to  $\leq$  5 mg/day
- Systemic CS dose > 5 to  $\leq$  7.5 mg/day
- Systemic CS dose > 7.5 to  $\leq$  10 mg/day
- Systemic CS dose > 10 to  $\leq$  20 mg/day
- Systemic CS dose > 20 mg/day
- Percent change in systemic CS dose at each study time point relative to baseline only in subjects on CS at baseline.
- Proportion of subjects in steroid-free quiescence at each study time point.
- Proportion of subjects in quiescence and for subjects without quiescence the proportion of subjects
  - with/without a change in concomitant medication (topical/systemic corticosteroids, immunosuppressants) within 5 days after non-quiescence and with/without quiescence at the next visit (at least 8 Weeks after non-quiescence)
  - with premature discontinuation
- OCT evidence of macular edema in at least one eye at each study time point.
- Central retinal thickness left/right eye and mean of both eyes at each study time point by OCT machine.
- Percent change in central retinal thickness (1 mm subfield) in each eye at each study time point relative to Baseline for subjects who had inactive uveitis when they entered the study and to Week 8 for subjects who had active uveitis when they entered the study.
- Change in NEI Visual Functioning Questionnaire (VFQ-25) score at each study time point relative to Baseline for subjects who had inactive uveitis when they entered the study and to Week 8 for subjects who had active uveitis when they entered the study.

For analysis of central retinal thickness, the central retinal thickness measured by the investigator will be used. Changes and percent changes in central retinal thickness may only be calculated for measurements from the same machine. Central retinal thickness

will be analyzed excluding patients with macular hole and/or rhegmatogenous retinal detachment affecting the macular.

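### The SAP's analysis of recovery after non-quiescence counts late or periocular-only rescue as no change in medication

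*SAP*

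**What the plan says.** SAP 10.2 divides subjects at a visit into quiescent and non-quiescent. It then splits the non-quiescent by whether they were "with/without a change in concomitant medication (topical/systemic corticosteroids, immunosuppressants) within 5 days after non-quiescence and with/without quiescence at the next visit". The parenthesis that follows requires that visit to lie 8 weeks or more after the non-quiescent finding. Premature discontinuation has its own line.

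The protocol allows more than the SAP rule counts:

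- **Route.** Protocol 5.2.3.2: "Subjects will be allowed two periocular corticosteroid injections per eye per year during the duration of the study at the investigator's discretion". Protocol 5.2.3.3 names systemic, topical and periocular corticosteroids side by side as exempt before it continues "corticosteroids as detailed in Section 5.2.3.2, the introduction of other medications for uveitis is prohibited during the study". Periocular is thus a separate permitted route, not part of topical or systemic. SAP 7.5 has a category "Other corticosteroids" for baseline therapy, but SAP 10.2 does not carry it into this analysis.
- **Timing.** Under Protocol 5.2.3.2, the immunosuppressant and corticosteroids "can be initiated, changed or discontinued during the course of the study if it is considered appropriate" in the investigator's opinion. No time limit after a flare is set.

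Nothing else in the SAP widens the 5-day window, adds a route, gives change a direction or plans a sensitivity analysis for this variable.

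**The concern.** The table pairs a statement about treatment with a statement about outcome, but the two cover different periods. The outcome is read after at least 56 days; the treatment is read over 5. A subject given only a periocular injection on the day of the finding, or whose prednisone is first raised on day 6 or in week 3, is reported as having had no change. If that subject is quiescent at reassessment, the label is false.

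The same wording also misplaces subjects in the other direction. A dose reduction within the 5 days is a change, so a subject who was tapered and still regained quiescence leaves the no-change group and joins the rescued.

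The study is open-label with one arm, and background therapy may be adjusted freely. Readers are likely to take recovery without a change as the result closest to control by the study drug. Its contents should match its label.

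**Working it through.** The plan attaches no sample size, power or event figure to this variable, so there is no stated figure to reproduce. The check is calendar arithmetic plus an illustration.

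**Inputs.** Visits at Weeks 0, 2, 4, 8, 12, 18 and every 12 weeks thereafter (SAP 4.2); a 5-day counting window and an 8-week minimum (SAP 10.2). I take reassessment to be the first later visit at least 8 weeks away, and assume that changes on the visit day count, which favours the plan.

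**Share of the interval covered** = 5 / days to reassessment.

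| Non-quiescent at | Reassessed at | Days | Covered | Not covered |
|---|---|---|---|---|
| Week 0 | Week 8 | 56 | 8.9% | 51 days (91.1%) |
| Week 2 | Week 12 | 70 | 7.1% | 65 days (92.9%) |
| Week 4 | Week 12 | 56 | 8.9% | 51 days (91.1%) |
| Week 8 | Week 18 | 70 | 7.1% | 65 days (92.9%) |
| Week 12 | Week 30 | 126 | 4.0% | 121 days (96.0%) |
| Week 18 onward | 12 weeks later | 84 | 6.0% | 79 days (94.0%) |

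If the SAP instead means that only an immediately following visit at least 8 weeks away qualifies, only the last row remains. With both visits allowed to move by 7 days, its interval runs from 70 to 98 days and coverage from 7.1% to 5.1%.

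**Scheduled visits inside the gap.** After non-quiescence at Week 12, the Week 18 visit comes before reassessment at Week 30, and a dose increase made there is not counted. The same holds for Weeks 2 and 4 after non-quiescence at Week 0, provided Week 0 is included, as the start at Baseline in SAP 10.1 suggests. A subject non-quiescent at Week 0, with prednisone raised at Week 2 and quiescent at Week 8, would be reported as recovered without a change.

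**A shorter denominator.** Protocol 5.1 says that a subject with an active flare for 4 weeks or more should be discontinued. Against those 28 days the window covers 5/28 = 17.9%, leaving 23 days (82.1%).

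**Illustration with assumed rates (none is in the documents).** Per 100 recoveries, let R follow a real start or increase, u be the share of those missed by the rule, and t be the share of the other recoveries with a taper within 5 days. Then

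reported no-change = (100 − R)(1 − t) + R·u.

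With R = 60 and t = 0, the true count is 40:

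- u = 10%: 40 + 6 = 46; mislabelled 6/46 = 13%
- u = 25%: 40 + 15 = 55; mislabelled 15/55 = 27%
- u = 50%: 40 + 30 = 70; mislabelled 30/70 = 43%

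Over R = 40 to 80 and u = 10% to 50%, the mislabelled share runs from 4/64 = 6% to 40/60 = 67%. The two errors cancel in the count when t = R·u/(100 − R). For R = 60 and u = 10% that is 6/40 = 15%; above it, the no-change cell is too small rather than too large. The range is wide because the inputs are unknown, so it shows the mechanism and not the size.

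**The case against.** The best defence is that 5 days is deliberate: it captures the treatment decision prompted by that finding. A window running to the next visit has its own error, since a drug started on day 80 for a new episode, or after quiescence had returned, would be attributed to the earlier one. This stands as a reason to keep the 5-day version. It does not explain the omission of periocular injections or the missing direction.

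Four stronger readings are tempting, and the documents do not support them.

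- A reader might infer that all rescued recoveries are reported as unaided. Subjects who start or increase a listed drug within 5 days are classified correctly, and the SAP does not attribute the no-change group to adalimumab.
- A reader might infer that 91% to 96% of rescue is missed. Treatment changes may well cluster at the visit where non-quiescence is found, so the share of days is not the share of rescue.
- A reader might infer that no other output bears on rescue. SAP 10.2 also plans steroid-free quiescence, systemic corticosteroid dose and dose bands, immunosuppressant starts and doses, and immunosuppression load. These describe therapy at or across visits, however; none is specified to link a given recovery to what was added after the preceding non-quiescent finding.
- A reader might infer that steroid-free quiescence ignores periocular injections too. The SAP leaves that term undefined, so the documents do not show it.

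Missed rescue that fails also enters the no-change row, so the recovery proportion within that row may shift less than the count of recoveries.

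**Conclusion.** The point holds in a limited form. As written, SAP 10.2 places late or periocular-only rescue in the no-change group, and those who then regain quiescence are wrongly counted as recovering without a medication change. This follows from the definition and needs no assumption about rates. A taper within 5 days is misplaced the opposite way.

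How many subjects are affected, and whether the no-change cell ends up too large or too small, cannot be determined from the documents. One might infer a one-way bias in favour of the drug, but that would need rates of late rescue, periocular-only rescue and early tapering that the documents do not give.

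The stakes are moderate. The variable is descriptive (SAP 10.1), the primary objective is safety (SAP 4.1), and this analysis has no planned graph or subgroup breakdown. It should be corrected because the label can be untrue and the data to correct it are already collected.

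**What to change.** In SAP 10.2:

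1. Add periocular and other corticosteroids to the medications whose change is counted.
2. Define change as a start or dose increase, and tabulate decreases separately.
3. Report the classification using any start or increase from the non-quiescent visit up to the visit at which quiescence is reassessed. Keep the 5-day version beside it as the immediate-response or sensitivity version.

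The cost is SAP wording and a little more programming. Protocol 5.2.3.2 already requires start and end dates, dose, frequency and route for every concomitant medication, so no new data are needed and clinical management is unaffected. The recovered-without-change cell is likely to be smaller in the full-interval version, which may also count some changes made for a later episode. Showing both versions lets a reader see how much the window matters.

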Subjects may be on only one of the allowed systemic immunosuppressants in addition to a systemic corticosteroid, at any timepoint.

Study visits will occur at Week 0, 2, 4, 8, 12, 18 and every 12 weeks thereafter. Efficacy assessments will be performed at every visit (Section 5.3.1). Both of the subject's eyes should be evaluated. **There will be no designated "study eye."**

Subjects who enter the study due to Treatment Failure in Study M10-877 or Study M10-880 and fail to achieve adequate control of their disease flare within the first 8 weeks may discontinue from the study.

Any other subject experiencing a uveitis flare during the study as determined by the investigator may discontinue from the study. Subjects may continue in the study, if it is determined by the investigator that the flare was triggered by a reduction or discontinuation in concomitant corticosteroid or systemic immunosuppressive therapy where further adjustment to the concomitant therapy may be warranted. Any subject continuing to have an active uveitis flare for 4 weeks or more should be discontinued from the study.

The site research staff will instruct and supervise subjects or a designee on proper injection technique at the scheduled visits. Subjects or a trained designee will administer adalimumab outside of clinic visits according to the specified dosing schedule.

An Independent Data Monitoring Committee (IDMC) will be established to independently monitor and assess data for Study M10-877, Study M10-880 and Study M11-327. The IDMC will be in effect until the end of both Study M10-877 and Study M10-880. At each committee meeting, the IDMC will undertake a comprehensive review and assessment of the cumulative safety data, which will include M11-327 study data.

Subjects may discontinue adalimumab treatment at any time during study participation. Subjects that end study participation early will have an Early Termination Visit. No study drug will be administered or injected at the final visit.

Safety data will be collected in the form of adverse events, physical examination, vital signs and laboratory tests throughout the treatment period and up to 70 days after the last injection in this study. All subjects will have a 70-day follow-up phone call or clinic visit to obtain follow-up information on any new or ongoing adverse events. The 70-day follow-up phone call will not be required for any subject that initiates commercial adalimumab after the end of study participation.

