5.2.2 Exclusion Criteria

1. A subject will be excluded from this study if the patient prematurely discontinued from Study M10-877 or Study M10-880 for any reason other than having a Treatment Failure event.
2. Subject with corneal or lens opacity that precludes visualization of the fundus or that likely requires cataract surgery during the duration of the trial.
3. Subjects with intraocular pressure of ≥ 25 mmHg and on ≥ 2 glaucoma medications or evidence of glaucomatous optic nerve injury.
4. This criterion has been removed.

5. Subject with proliferative or severe non-proliferative diabetic retinopathy or clinically significant macular edema due to diabetic retinopathy.
6. Subject with neovascular/wet age-related macular degeneration.
7. Subject with abnormality of vitreo-retinal interface (i.e., vitreomacular traction, epiretinal membranes, etc.) with the potential for macular structural damage independent of the inflammatory process.
8. Subject with a systemic inflammatory disease that requires therapy with a prohibited immunosuppressive agent at the time of study entry.
9. This criterion has been removed.
10. This criterion has been removed.
11. This criterion has been removed.
12. Female subjects who are pregnant or breast-feeding or considering becoming pregnant during the study.
13. Evidence of dysplasia or history of malignancy (including lymphoma and leukemia) other than a successfully treated non-metastatic cutaneous squamous cell, basal cell carcinoma or localized carcinoma in situ of the cervix.
14. Subject is considered by the Investigator, for any reason, to be an unsuitable candidate for the study (for example, abnormal laboratory results).
15. Subjects with infection(s) requiring treatment with intravenous (IV) anti-infectives within 30 days prior to the Baseline visit or oral anti-infectives within 14 days prior to the Baseline visit.
16. Subject with an active systemic viral infection or any active viral infection that based on the investigator's clinical assessment makes the subject an unsuitable candidate for the study.

Rationale for Exclusion Criteria:

- a. The following criteria were implemented to select the appropriate subject population for evaluation: 1-8.
- b. The following criterion was implemented because the impact of adalimumab on pregnancy is unknown: 12.
- c. The following criteria were implemented for safety of the subjects: 13-16.

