5.3.3 Efficacy Variables

Efficacy will be determined at each visit by the following criteria. Both of the subjects' eyes will be assessed. The following endpoints will be used to evaluate the long-term efficacy of adalimumab to treat subjects with non-infectious intermediate-, posterior-, or pan-uveitis.

- Proportion of subjects at each study time point with no new active, inflammatory chorioretinal or inflammatory retinal vascular lesion in both eyes relative to Baseline for subjects who had inactive uveitis when they entered the study and to Week 8 for subjects who had active uveitis when they entered the study.
- Proportion of subjects at each study time point with a Grade $\leq 0.5+$ in AC cells in both eyes on Slit Lamp Exam according to SUN criteria.
- Proportion of subjects at each study time point with a Grade $\leq 0.5+$ in vitreous haze in both eyes on indirect ophthalmoscopy according to NEI/SUN criteria.
- Proportion of subjects at each study time point without a worsening of BCVA by ≥ 15 letters on the ETDRS in both eyes relative to Baseline for subjects who had inactive uveitis when they entered the study and to Week 8 for subjects who had active uveitis when they entered the study.
- Percent change in central retinal thickness (1 mm subfield) in each eye at each study time point relative to Baseline for subjects who had inactive uveitis when they entered the study and to Week 8 for subjects who had active uveitis when they entered the study.
- Change in NEI Visual Functioning Questionnaire (VFQ-25) score at each study time point relative to Baseline for subjects who had inactive uveitis when they entered the study and to Week 8 for subjects who had active uveitis when they entered the study.
- Proportion of subjects at each study time point achieving a $\geq 50\%$ reduction in immunosuppression load relative to Baseline for subjects who had inactive

uveitis when they entered the study and to Week 8 for subjects who had active uveitis when they entered the study.⁴⁰

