6.1.1.1.1 Uveitis-Related Events

The following events are known complications related to the condition being treated and will be classified as uveitis-related events. These events will be analyzed separately from other adverse events in the final study report.

The following events are not a complete list of all potential uveitis-related events (e.g., choroidal thickening, choroidal detachment, retinal effusion, are not included but could possibly be events related to uveitis). The investigator must determine if a specific event is uveitis-related.

- Loss of transparency of the cornea
- Band keratopathy
- Synechiae
- Cataracts
- Glaucoma/increased intraocular pressure
- Vitreous hemorrhage
- Macular edema
- Retinal detachment
- Epiretinal membrane
- Vitreo-macular traction
- Retinal ischemia
- Vision loss
- Hypotony

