- Vitreous haze grades (NEI/SUN criteria) (continuous and categorical)
- LogMAR Best corrected visual acuity (BCVA) will be calculated as follows:
  - if  $\geq$  20 letters were read at 4 m OR if < 20 letters were read at 4 m but the test was not done at 1 m,  
$$\text{logMAR} = 1.7 - 0.02 * (\text{number of letters read at 4 m} + 30),$$
  - if < 20 letters were read at 4 m and the test was also done at 1 m,  
$$\text{logMAR} = 1.7 - 0.02 * (\text{number of letters read at 4 m} + \text{number of letters read at 1 m})$$
  - if 0 letters were read at 1 m, the following logMAR values will be calculated according to Holladay (1997):
    - in case of finger counting:  
$$\text{logMAR} = (-1) * \log_{10}(\text{distance in meters}/60)$$
    - in case of hand movements:  $\text{logMAR} = 3.0$
- Power of sphere (diopters)
- Power of cylinder (diopters)
- Axis of cylinder (degrees)

For analysis of central retinal thickness, the central retinal thickness measured by the investigator will be used. Central retinal thickness will be analyzed by OCT machine. Central retinal thickness and macular edema will be analyzed excluding patients with macular hole and/or rhegmatogenous retinal detachment affecting the macular. OCT evidence of macular edema will be defined as center point thickness  $\geq$  260 microns for Stratus,  $\geq$  320 microns for Cirrus,  $\geq$  340 microns for Spectralis.

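### The OCT exclusion for macular hole or macula-involving detachment is written per patient, with no limit to the affected eye or to visits from onset

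*SAP*

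**What the plan says.** SAP 10.2 says that central retinal thickness "will be analyzed excluding patients with macular hole and/or rhegmatogenous retinal detachment affecting the macular". SAP 7.1, on baseline characteristics, has a wider sentence: "Central retinal thickness and macular edema will be analyzed excluding patients with macular hole and/or rhegmatogenous retinal detachment affecting the macular". Neither section mentions the affected eye, a date of onset, or whether the condition must be present at entry.

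The variables concerned are defined by eye and visit. SAP 10.2 lists "Percent change in central retinal thickness (1 mm subfield) in each eye at each study time point" and "Central retinal thickness left/right eye and mean of both eyes at each study time point by OCT machine", plus OCT evidence of macular edema in one or both eyes. Protocol 5.3.3 defines the change variable in the same way ("Percent change in central retinal thickness (1 mm subfield) in each eye at each study time point relative to Baseline") and contains no such exclusion. Protocol 5.1 names no study eye and asks that both eyes be evaluated. Protocol 5.3.1.1 requires OCT at every visit.

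Retinal detachment is on the list that Protocol 6.1.1.1.1 introduces with "The following events are known complications related to the condition being treated and will be classified as uveitis-related events", and SAP 11.1 repeats that list.

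**The concern.** There is good reason to drop an eye with a macular hole or a detached macula: its thickness reading may not be interpretable. That reason does not extend to the other eye, or to the same eye before the event.

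If patients are removed, two things follow. Valid measurements are lost. And if the condition can arise on study, membership of the analysis at an early visit is decided by something that happens later, so the early-visit mean is conditioned on a future retinal event.

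The sentence can also be programmed in more than one way (patient or eye; ever, at baseline or from onset), so two programmers could produce different tables from it.

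**Working it through.** The plan gives no figure to reproduce. The study is single-arm, all efficacy analyses are descriptive (SAP 10.1), and there is no sample-size calculation (Protocol 8.2). The check is a reading of the text followed by bookkeeping.

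**Unit and timing.** The endpoint is per eye and per visit, while the exclusion is per patient. SAP 5.1 states timing where it means to: it refers to cataract surgery during the study, and to vitrectomy either previous or during the study. The OCT sentence is silent. Onset on study is realistic, because retinal detachment is a listed uveitis-related event. Protocol 5.2.2 also excludes at entry vitreo-retinal interface abnormalities "with the potential for macular structural damage independent of the inflammatory process", so some macular risk is screened out beforehand.

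**Readable share of removed eye-visits, one-eye event.** Let t be the share of visits before the event. The patient rule removes both eyes at all visits. Only the affected eye from the event onward is unreadable, which is 0.5 × (1 − t) of the total.

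Readable share = 1 − 0.5 × (1 − t)

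- t = 0.25: 1 − 0.375 = 0.625
- t = 0.50: 1 − 0.250 = 0.750
- t = 0.75: 1 − 0.125 = 0.875

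**On the actual schedule.** Visits to Week 66 are Weeks 0, 2, 4, 8, 12, 18, 30, 42, 54 and 66: 10 visits, or 20 eye-visits.

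- Event after half the visits: 5 unreadable eye-visits, so 15/20 = 75% readable.
- Event at the calendar midpoint (Week 33): 7 visits come before it and 3 after, so 17/20 = 85% readable. The early visits are closely spaced, so the calendar midpoint falls late in the visit count.
- To Week 378, the last week printed in the dosing diary (Protocol Appendix E): 36 visits, 72 eye-visits. After half the visits, 54/72 = 75%. At Week 189, 20 visits come before and 16 after, so 56/72 = 78%.

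**Subjects and effect on the mean (illustration only).** The documents give no incidence. Assume N = 400 (the planned enrolment), a share q = 0.5% to 3% affected, and one eye each.

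- Subjects removed: q × N = 2 to 12.
- Eyes removed under the patient rule: 2qN = 4 to 24.
- Eyes removed under an eye rule: qN = 2 to 12. Half of the eyes dropped by the patient rule are fellow eyes.
- Shift in mean percent change: q × D, where D is the difference between excluded and retained eyes. For D = 10 to 50 points, the shift runs from 0.005 × 10 = 0.05 to 0.03 × 50 = 1.5 points.

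Both q and D are assumptions.

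**The case against.** The best reply is that the SAP nowhere says both eyes and all visits. The fuller sentence sits in the baseline section, and thickness is summarised by eye, so a baseline-only or visit-by-visit application is open. That stands as a limit: the wider removal is the plain reading of a patient-level rule with no time limit, but it is not explicit. It does not rescue the text, because under any reading the unit and timing still have to be written down.

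A reader might infer that poor retinal outcomes are being hidden. The documents do not support that. Retinal detachment and vision loss are reported as uveitis-related adverse events in the safety set, and the visual acuity variables carry no such exclusion.

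A reader might also infer that thickness and edema at follow-up use different subjects, since SAP 10.2 repeats the rule for thickness only. That is arguable at most. SAP 7.1 already covers edema, and the same paragraph holds the only definition of OCT evidence of edema, on which 10.2 depends.

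The number of subjects is weakly supported. Macular hole is not on the listed events, and the list covers any retinal detachment whereas the rule covers only rhegmatogenous detachment of the macula. Any affected subject who has a vitrectomy is already outside the ITT set under SAP 5.1.

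Finally, simply setting the affected eye to missing would not work. LOCF (SAP 6.3.2) would carry its pre-event thickness forward, NRI (SAP 6.3.1) would count it for edema, and the two-eye variables would be undefined. That objection is right and shapes the fix.

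**Conclusion.** The point holds as a minor one. The rule is set at patient level for an eye-level variable and has no onset limit. Followed as written, it drops readable data and lets a possible later event decide who contributes to earlier means.

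For a one-eye event midway, about 75% of the removed eye-visits would be readable with evenly spaced visits, and about 85% at the calendar midpoint of the schedule to Week 66. These shares assume a one-eye event and complete follow-up. The number of subjects affected is unknown and may partly overlap the vitrectomy exclusion. The effect on any mean is probably small (0.05 to 1.5 points under the assumed inputs).

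Only descriptive OCT results are involved, not the primary safety objective. The documents support neither a claim that bad outcomes disappear from the trial's results nor a firm claim that removal at all visits was intended.

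**What to change.** In SAP 7.1 and 10.2:

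- Exclude only the affected eye, as not evaluable, from the first visit at which the macular hole or macula-involving rhegmatogenous detachment is recorded. Keep the fellow eye and all earlier visits.
- State that excluded eye-visits are not filled by LOCF and not counted by NRI.
- Calculate the two-eye mean only when both eyes are evaluable, and base edema in at least one eye on the evaluable eye or eyes.
- Apply the same rule, in words, to thickness and macular edema in both sections.
- Report the number of eyes and of subjects excluded.

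The cost is a short paragraph in the SAP and slightly more programming. The eye and the first-recorded visit must be identifiable, and the documents do not show that they are: the adverse event items listed in Protocol 6.1 do not include the eye. Where the eye cannot be identified, exclude both eyes from the first-recorded visit.
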